3.4. Safety Assessment

Safety will be assessed by monitoring adverse events, changes in PEs (including vital signs), changes in ECGs, and changes in laboratory parameters. Safety assessments will take place every 4 weeks during study participation.

Classic CAH subjects will have been enrolled into the study on stable glucocorticoid and mineralocorticoid regimens. Monitoring and management of replacement steroids should continue per usual clinical practice.

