3.5. Criteria for Study Termination

The study is open-label and all laboratory results will be able to be viewed by the Investigator and Sponsor. The Sponsor will review pooled and individual subject data at regular intervals during the course of the study. In addition, a single occurrence of any the following safety events will trigger an expedited, *ad hoc* safety meeting of at least the Sponsor and the Medical Monitor:

- Marked elevations in transaminases or simultaneous elevations in hepatic transaminases and bilirubin (i.e., Hy's Law)
- Severe renal impairment
- Severe cardiovascular dysfunction such as arrhythmia or valvular dysfunction, or New York Heart Association (NYHA) Class III or IV heart failure.

If the Sponsor and the Medical Monitor determine that the event is drug-related and a clear safety signal has been identified, the Sponsor and the Medical Monitor will determine whether early termination of the study is warranted.

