6.11.1. Clinical Laboratory Assessments

Testing of clinical laboratory samples will be carried out by the central clinical laboratory using validated methods and will include the tests listed in [Table 3](#). In addition, stored serum and plasma samples may be assayed for parameters relevant to hormone metabolism (no DNA samples will be stored). Total blood volumes to be collected will be provided in the Laboratory Manual. Abnormal, clinically significant results may be verified to rule out laboratory error. Persistent relevant abnormal values must be followed up until the cause is determined or until they return to the baseline value. Abnormal laboratory findings that are considered clinically significant by the Investigator should be recorded as AEs as appropriate ([Section 6.10](#)).

Table 3: List of Clinical Laboratory Tests

Hematology	hematocrit (Hct), hemoglobin (Hgb), platelet count, red blood cell (RBC) count, white blood cell (WBC) count with differential
Chemistry	albumin, alkaline phosphatase, alanine aminotransferase (ALT; SGPT), aspartate aminotransferase (AST; SGOT), blood urea nitrogen (BUN), calcium, creatinine, glucose, total bilirubin, total protein, electrolytes (magnesium, sodium, potassium, chloride, bicarbonate)
Coagulation	PT, aPTT, INR
Plasma or Serum Hormones	17-hydroxyprogesterone, androstenedione, adrenocorticotrophic hormone, cortisol, progesterone, total testosterone, and 11-ketotestosterone
Salivary Hormones	17-hydroxyprogesterone, progesterone (premenopausal women “08:00” sample only), and cortisol (“08:00” sample only)
Urinalysis	appearance, bilirubin, color, glucose, ketones, leukocyte esterase, nitrite, occult blood, pH, protein, specific gravity, urobilinogen; microscopic examination will be performed if leukocyte esterase, nitrite, and/or occult blood are positive
Other	HBsAg, HCV, HIV, urine drug screen

aPTT, activated partial thromboplastic time; HBsAg, hepatitis B surface antigen; HCV, hepatitis C virus; HIV, human immunodeficiency virus; INR, international normalized ratio; PT, prothrombin time

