The nevanimibe 1500 mg BID and 2000 mg BID doses in this CAH Phase 2b study are supported by the ACC Phase 1 MTD study (N=63) with long-term exposures and extensive PK data. The ACC Phase 1 MTD study used a dose range of 1.6 to 158.5 mg/kg/day (equivalent to approximately 11,900 mg/day for a 75-kg individual). Multiple conditions for oral administration were used in attempts to increase nevanimibe exposure to the greatest extent possible. A once daily, powder-in-capsule formation was used for the first 7 dose cohorts; a tablet formulation twice per day (BID) with a non-diet cola to maintain acidic stomach conditions was used for Cohorts 8 to 11; and Cohorts 12-14 were dosed with food BID. Even at the highest dose (158.5 mg/kg/day) a MTD could not be defined as dose-limiting toxicities (DLT) did not occur. Only two DLTs were reported during the entire study: a grade 3 elevation of liver enzymes in a subject with pre-existing liver disease (occurring at 102.4 mg/kg/day) and grade 3 vomiting and diarrhea (occurring at 37.3 mg/kg/day). Some “hints” of efficacy were reported with prolonged periods of stable disease observed in multiple subjects (Figure 1). Although a MTD could not be defined, the Sponsor voluntarily halted the study due to low grade, chronic gastrointestinal side effects (e.g., nausea, diarrhea) secondary to the large number of tablets required (i.e., 158.5 mg/kg/day = ~24 tablets per day, each 500 mg tablet being 19 mm x 8 mm in size). A dose of 128.2 mg/kg/day (equivalent to approximately 9600 mg/day for a 75-kg individual) was declared as the “maximum feasible dose” that could be taken on a long-term, chronic basis. This dose is approximately 2.5x higher than the highest dose being used in the CAH Phase 2b study. Thus, the ACC data provides a wide safety margin.

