The mean time to onset of AEs (including worsening of preexisting conditions) will additionally be presented using summary statistics for continuous variables, overall and by SOC and PT. Time to first treatment-related TEAE and/or onset of selected TEAEs/groups of TEAE, may further be displayed in a Kaplan-Meier curve(s), by dose and/or in total, and by cohort and in total, where the time reflects the number of days since first being treated with the corresponding dose and changes to the dose will be included as censored information. If a subject is treated at a certain dose, then the dose is changed and at a later point, the subject is treated with the same dose again, then the duration of treatment with said dose will be added to the initial treatment period. Serious adverse events (SAEs) as well as AEs leading to death or discontinuation will be listed. Additionally, SAEs will be summarized overall and by nevanimibe dose.

Laboratory assessments, physical examinations, ECG and vital signs will be evaluated as continuous or categorical variables according to standard summary statistics for each visit, overall. Changes from baseline will be calculated for continuous variables and shift tables depicting the change from baseline will be produced for categorical variables where applicable and meaningful.

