7.10 Special Analytical Issues

Data from unscheduled visits will only be listed except for data regarding AEs, concomitant medications and medical history.

Subject doses will be allocated unambiguously into the following categories for the analysis by dose:

- <500 mg BID
- 500 mg BID to <1000 mg BID
- 1000 mg BID to <1500 mg BID
- 1500 mg BID to <2000 mg BID
- 2000 mg BID

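### Liver-test peaks seen only at unscheduled draws are left out of every laboratory summary table, and no planned table pairs transaminases with bilirubin within a subject

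*SAP*

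**What the plan says.** **The trigger.** Protocol 3.5 states that "a single occurrence of any the following safety events will trigger an expedited" ad hoc meeting of at least the sponsor and the Medical Monitor, who may then decide to end the study. First on its list is "Marked elevations in transaminases or simultaneous elevations in hepatic transaminases and bilirubin", labelled as Hy's Law. No multiples of ULN and no time window are given.

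**When liver tests are drawn.** Protocol 3.4: "Safety assessments will take place every 4 weeks during study participation". Off-schedule draws are foreseen. Protocol 6.11.1 allows clinically significant abnormal results to be verified and adds: "Persistent relevant abnormal values must be followed up until the cause is determined or until they return to the baseline value".

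**How they are analysed.** Under SAP 7.7, laboratory data "will be evaluated as continuous or categorical variables according to standard summary statistics for each visit, overall", with changes from baseline and, where meaningful, shift tables. SAP 7.10 then says: "Data from unscheduled visits will only be listed except for data regarding AEs, concomitant medications and medical history". Laboratory values are not among the exceptions.

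**Planned outputs (SAP Appendix 1).** Table 14.3.3.1 (blood chemistry), the 14.3.3.7 chemistry shift tables and Listing 16.1.3.2. Protocol 9.6.2 has the same form: summaries by time point, plus shift tables.

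**The concern.** Safety is part of the primary objective, and the liver condition heads the protocol's own list of safety triggers. The draws most likely to hold a peak, or to confirm one, are those taken outside the schedule because a value was abnormal or the subject was unwell. The 7.10 rule keeps exactly those draws out of the summaries. The next scheduled value may already be a recovery value, particularly as protocol 5.3.3 lets the dose be lowered or interrupted for safety between visits.

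Separately, a summary of each analyte by visit cannot show whether high transaminases and high bilirubin belong to the same subject. A reader of the laboratory tables in the study report could not tell whether the protocol 3.5 condition occurred.

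**Working it through.** The plan gives no figure on this point to reproduce. The check compares the texts and adds supporting arithmetic.

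**1. Which values enter which output**

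| Value | By-visit chemistry table | Shift tables | Listing 16.1.3.2 | Adverse event tables |
|---|---|---|---|---|
| Scheduled visit, including F1 | yes | yes, where produced | yes | only if recorded as an AE |
| Unscheduled visit | no (7.10) | no (7.10) | yes | only if recorded as an AE |
| Worst value per subject | not planned | not planned | by hand | no |
| ALT/AST with bilirubin, same subject | not planned | not planned | by hand | no |

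SAP 7.1 includes the maximum in its default statistics, so a peak at a scheduled visit can appear as the group maximum for that visit. The maximum ALT and the maximum bilirubin may come from different subjects.

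The shift-table categories and comparison visit are not defined in the text. If they were low/normal/high (an assumption), a subject who entered above ULN and then rose much further would stay in the high category. Exclusion criterion 6 allows such entry, with ALT/AST up to 2x ULN and bilirubin up to 1.5x ULN.

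**2. Spacing of scheduled chemistry**

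Days 1, 29, 57, 85, 113 (amendment 1), and also 141 (amendment 2). Differences: 29 − 1 = 57 − 29 = 85 − 57 = 113 − 85 = 141 − 113 = 28 days.

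The documents do not say how long an elevation would last. Assume D days with onset at random relative to the visits. The chance that a scheduled draw falls within it is min(1, D/28):

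- D = 7: 7/28 = 25%
- D = 14: 14/28 = 50%
- D = 21: 21/28 = 75%

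This is the chance of meeting the elevation at all, not of meeting its peak.

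**3. What one case means at this size**

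The plan is for about 20-24 evaluable subjects (protocol 9.2); 24 is used here.

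- One case: 1/24 = 4.2%. Clopper-Pearson 90% limits: lower = 1 − 0.95^(1/24) = 0.2%; upper solves (1 − p)^24 + 24p(1 − p)^23 = 0.05, giving p = 18.3%.
- No case: 90% upper limit = 1 − 0.05^(1/24) = 11.7%.
- Chance of at least one case, 1 − (1 − p)^n, for n = 20 to 24: 18-21% at an assumed true rate of 1%, 33-38% at 2%, 64-71% at 5%.

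These figures show that a single case carries weight in so small a trial. They do not measure how often a peak would fall only at an unscheduled draw. The documents give nothing from which to estimate that.

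**The case against.** The strongest reply is that little is hidden.

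- **Adverse events.** SAP 7.10 exempts AE data from the listing-only rule. Protocol 6.10.1 says that laboratory abnormalities leading to withdrawal of treatment or to added treatment should be AEs, and 6.11.1 asks for clinically significant findings to be recorded as AEs where appropriate. A serious liver event found off schedule would be expected to reach the 14.3.1 tables and, if serious, the SAE outputs. This stands. But the route depends on investigator judgement and coding, and it does not apply the 3.5 condition. The AE tables by dose also count a subject at the lowest dose on which the AE occurred, which need not be the dose at the peak.
- **Listings.** With 20-24 subjects, Listing 16.1.3.2 can be read by hand. This stands, and it limits the weight of the point. A hand reading is not a prespecified count.
- **Real-time oversight.** Protocol 3.5 is an operational trigger. The sponsor sees all laboratory results and reviews individual data during the study. This stands: a table made after lock would not change how the trigger works, only what the report can state.
- **Prior signal.** Protocol Appendix 7 cites "a grade 3 elevation of liver enzymes in a subject with pre-existing liver disease", but at 102.4 mg/kg/day, against about 53 mg/kg/day at this trial's highest dose for a 75-kg subject (102.4/53 = 1.9 times). It also reports no notable safety events in the earlier CAH study. The case is weak support for expecting liver events here, and the point does not rest on it.
- **Consistency.** SAP 7.7 follows protocol 9.6.2, so the two documents do not contradict each other. This stands.

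A reader might infer that a trigger-level event seen only off schedule would be reported as zero cases in 24, or would vanish from the report. The documents do not support that. No planned table counts the condition, so none can display a zero, and the AE tables and the listing remain open. Nor are all values after treatment excluded: Visit F1 is scheduled, includes chemistry and is summarised.

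**Conclusion.** The point holds as a gap in tabulation. By the stated rules, an ALT, AST or bilirubin peak seen only at an unscheduled visit enters no laboratory summary table. No planned table gives a worst value per subject or pairs transaminases with bilirubin within a subject, although protocol 3.5 gives a single such case the weight of an expedited meeting.

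The consequence is moderate. The information can be recovered from the listing and possibly from the AE tables, and no efficacy result is touched. How often the gap would matter cannot be calculated; the 25% to 75% range above rests on assumed durations and random onset.

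Two limits apply. The mock tables were not available, so shift-table categories could not be checked, although under 7.10 those tables would still omit unscheduled values. And protocol 3.5 sets no numerical definition, so the condition cannot yet be tabulated as it stands.

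**What to change.** Before database lock:

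1. In SAP 7.10, except ALT, AST and total bilirubin from the listing-only rule.
2. In SAP 7.7 and Appendix 1, add one Safety Population table. For each subject, show the worst ALT, AST and total bilirubin after the first dose as multiples of ULN, from all samples (scheduled, unscheduled and early termination). Include a flag for concurrent ALT/AST and bilirubin elevation, and the nevanimibe dose at the time of the peak.
3. State in the SAP the analysis definition behind the flag: the cut-offs and the time window that counts as concurrent. The sponsor has to choose these, because protocol 3.5 gives neither. The definition serves the table only and leaves the clinical trigger unchanged.

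The cost is a short SAP amendment, agreement on the definition, and one table from laboratory data already collected. The downside is that worst-value tables pick up transient or spurious results, so the verified repeat should be shown beside each peak.

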7.8 Evaluation of Pharmacokinetic Variables

Pharmacokinetic parameters (C_{last} , C_{max} , C_{max}/D , T_{max} , AUC_{0-4} , AUC_{0-4}/D , AUC_{0-t} , λ_z , $t_{1/2}$, $AUC_{0-\infty}$, $AUC_{\%extrap}$, CL/F) for nevanimibe and its major metabolite(s) will be computed as data permit and as appropriate

using non-compartmental methods employing WinNonlin® Phoenix version 6.3 or later (Pharsight Corp., Mountain View, CA). PK parameters may also be estimated for replacement glucocorticoids and/or mineralocorticoids as appropriate.

The pharmacokinetic analyses will be described in detail in a separate PK Analysis Plan by Certara USA, Inc. (Princeton, New Jersey, USA) as it will be conducted separately from the analyses described in this document.

7.9 Evaluation of Other Variables

Study drug compliance will be evaluated for the safety population according to the counts of number of tablets dispensed and number of tablets returned, along with the assigned doses of study drug, as recorded in the eCRF. The compliance will be calculated for Visit T1 (Day 1) – Visit T2 (Day 29), Visit T2 (Day 29) – Visit T3 (Day 57), Visit T3 (Day 57) – Visit T4 (Day 85), Visit T4 (Day 85) – Visit T5 (Day 113) and overall (Visit T1 (Day 1) – Visit T4/T5 (Day 85/113)(or early termination date)) as follows:

$$\Delta = (\text{Number of tablets the subject should have taken (based on assigned dose level(s))} - \text{Number of tablets taken})$$

$$\text{Compliance} = \left(1 - \frac{\Delta}{\text{Number of tablets the subject should have taken}}\right) \times 100\%$$

Overall compliance for amendment 1 patients will be calculated from Visit T1 to Visit T4 or early study termination date, while compliance for amendment 2 patients will be calculated from Visit T1 to Visit T5 or early study termination date.

The duration of exposure will be calculated as follows:

$$\text{Duration} = (\text{Date of last dose of study drug} - \text{date of first dose of study drug}) + 1$$

The mean duration of exposure will be calculated overall, by amendment and by cohort.

The duration of treatment in subject-years will be calculated by cohort and by nevanimibe dose as the sum of the duration of exposure of all subjects, overall or in the respective cohort or nevanimibe dose.

All information recorded in the eDiary, including the usage of glucocorticoids and mineralocorticoids, will be listed only.

7.10 Special Analytical Issues

Data from unscheduled visits will only be listed except for data regarding AEs, concomitant medications and medical history.

Subject doses will be allocated unambiguously into the following categories for the analysis by dose:

- <500 mg BID
- 500 mg BID to <1000 mg BID
- 1000 mg BID to <1500 mg BID
- 1500 mg BID to <2000 mg BID
- 2000 mg BID

7.10.1 Interim Analysis

No Interim analysis will be performed.

8. Changes in the Planned Analyses

Changes made to the planned analyses in the clinical study protocol as of the finalization of this SAP (version 1.0) are as follows:

- The PPP definition has been updated to additionally stipulate that the subjects were in the treatment period of the study for at least 56 days and were compliant with study drug administration.

Any additional changes to the planned analyses in the clinical study protocol or the SAP decided before final database lock at the end of the study and the reasoning will be described in amendments to the clinical study protocol and/or the SAP and will be detailed in the clinical study report (CSR). Any exploratory analyses conducted in addition to the analyses described in the SAP after final database lock at the end of the study and the reasoning will be clearly highlighted and discussed in the clinical study report.

9. APPENDIX 1

The following lists give an overview of the required tables, figures and listings. Numbering and titles are not obligatory, and changes may occur after agreement of the sponsor. The changes, however, should not contradict the planned analyses described in this SAP. Any post-hoc analyses not defined in the final version of the study protocol/amendment or the SAP may be implemented as exploratory analyses and will be clearly identified as not planned in advance.

For additional information on the layout of the tables and listings, refer to the mock tables or mock listings documents.

Tables

14.1	Study Subjects
14.1.1	Disposition of Subjects
14.1.1.1	Subject Disposition, by Cohort and in Total
14.1.1.2	Number of Subjects per Visit, by Site and in Total
14.1.2	Demographics and Other Baseline Characteristics
14.1.3	Medical History
14.1.4	Previous and Concomitant Medications
14.1.4.1	Previous Medications, by ATC Level
14.1.4.2	Concomitant Medications, by ATC Level
14.1.5	Study Drug Exposure and Compliance
14.2	Efficacy Data
14.2.1.	Primary endpoint
14.2.1.1	Serum 17-Hydroxyprogesterone Responder Rate, by Visit
14.2.1.2	Serum 17-Hydroxyprogesterone Concentrations, by Visit
14.2.1.3	Change in Serum 17-Hydroxyprogesterone, by Visit
14.2.1.4	Summary of Serum 17-Hydroxyprogesterone, by Visit
14.2.1.5	Summary of Serum 17-Hydroxyprogesterone Repeated Measurements, by Visit
14.2.2	Secondary endpoints
14.2.2.1	Summary of Salivary 17-Hydroxyprogesterone Repeated Measurements, by Visit
14.2.3.1	Serum Androstenedione Concentration, by Visit
14.2.3.2	Summary of Serum Androstenedione, by Visit
14.2.4	Serum Progesterone, by Visit
14.2.5	Total Testosterone, by Visit
14.2.6	11-keto Testosterone, by Visit

- 14.3 Safety Data
 - 14.3.1 Adverse Events
 - 14.3.1.1 Overview of Treatment-Emergent Adverse Events, by Dose Level and Overall
 - 14.3.1.2 Treatment-Emergent Adverse Events by Dose Level and Overall
 - 14.3.1.2.1 Treatment-Emergent Adverse Events by Dose Level and Overall, by Preferred Term, Alphabetically
 - 14.3.1.2.2 Treatment-Emergent Adverse Events by Dose Level and Overall, by Preferred Term, by Frequency
 - 14.3.1.3 Treatment-Emergent Adverse Events by Dose Level and Overall, by Time Range
 - 14.3.1.4 Treatment-Emergent Adverse Events by Dose Level and Overall, by System Organ Class and Preferred Term, and Maximum Severity
 - 14.3.1.5 Treatment-Emergent Adverse Events Related to Study Drug by Dose Level and Overall, by System Organ Class and Preferred Term
 - 14.3.1.6 Treatment-Emergent Adverse Events Related to Study Drug by Dose Level and Overall, by System Organ Class and Preferred Term, and Maximum Severity
 - 14.3.1.7 Average Time to Treatment-Emergent Adverse Event
 - 14.3.2 Serious Adverse Events and Adverse Events Leading to Death or Discontinuation
 - 14.3.2.1 Listing of Treatment-Emergent Serious Adverse Events
 - 14.3.2.2 Listing of Treatment-Emergent Adverse Events Leading to Discontinuation from Study
 - 14.3.2.3 Listing of Treatment-Emergent Adverse Events Leading to Death
 - 14.3.3 Other Safety Parameters
 - 14.3.3.1 Blood Chemistry
 - 14.3.3.2 Plasma ACTH and Serum Cortisol
 - 14.3.3.3 Hematology
 - 14.3.3.4 Coagulation Parameters
 - 14.3.3.5 Urinalysis
 - 14.3.3.6 Salivary Cortisol and Progesterone
 - 14.3.3.7 Blood Chemistry, Shift Tables
 - 14.3.3.7.1 Blood Chemistry, Shift Tables, Part 1
 - 14.3.3.7.2 Blood Chemistry, Shift Tables, Part 2

Listings

- 16.1 Subject Data Listings
 - 16.1.1 Study Subjects
 - 16.1.1.1 Disposition of Subjects
 - 16.1.1.1.1 Screening Failures
 - 16.1.1.1.2 Study Progress Overview

16.1.1.1.3	Site Numbers and Principle Investigators
16.1.1.1.4	Visit Dates and Discontinuation
16.1.1.2	Eligibility and Protocol Deviations
16.1.1.2.1	Subjects with Violation of Inclusion / Exclusion Criteria
16.1.1.2.2	Protocol Deviations and Other Reason for Exclusion from Analysis Sets, Assignment to Analysis Sets
16.1.1.3	Demographic Data and Other Baseline Characteristics
16.1.1.3.1	Demographics and Other Baseline Characteristics
16.1.1.3.2	Findings in Medical History
16.1.1.3.3	Findings in Prior Medication
16.1.1.3.4	Findings in Concomitant Medication
16.1.1.4	Study Drug Administration, by Visit
16.1.2	Efficacy Data
16.1.2.1	Serum 17-Hydroxyprogesterone
16.1.2.2	Salivary 17-Hydroxyprogesterone
16.1.2.3	Serum Androstenedione
16.1.2.4	Serum Progesterone
16.1.2.5	Total Testosterone
16.1.2.6	11-keto Testosterone
16.1.3	Safety Data
16.1.3.1	Adverse Events
16.1.3.2	Blood Chemistry
16.1.3.3	Plasma ACTH and Serum Cortisol
16.1.3.4	Hematology
16.1.3.5	Coagulation Parameters
16.1.3.6	Urinalysis
16.1.3.7	Salivary Cortisol and Progesterone

Figures

14.1.1.1	Subject Disposition, by Cohort and in Total
14.2.1.1	Dose-Response Relationship
14.3.1.7	Time to First Treatment-Emergent Adverse Event, by Dose
